1.3 Schedule of Activities

Table 1 Schedule of Activities - Part A (M3814 + Avelumab)

		Treat	ment	Perio	d: M3	3814+	avelumab	End	of Trea	atment	(EoT)/FU	Notes
Study Period	Screening	DL	.T Peri	iod				EoT	Safe	ty FU	Long-term FU	
Visit	-1	1	2	3	4	5	n				Q12W	During on-treatment period, after Day 29, visits
Study Day (± Visit window)	-28 to -1	1	15 (± 1)	22 (± 1)		43 (± 1)	n + 14 d (± 2)	(Within 7 days of decision to disconti nue)	(± 5)	2 90 d (± 5)	(± 7)	will be every 2 wks on days of avelumab infusions until EoT. All participants discontinuing study interventions for any reason must undergo EoT Visit within 7 days after decision to discontinue study interventions, but (if possible) before any new antineoplastic therapy is started. The safety follow-up period will be 30 days (± 5 days) after the last dose of avelumab, see Section 4.1.1.3.
M3814		Cont	inuou	s BID	dosi	ing (7	days/wk)					See Section 6.6.5.1 for details.
Premedication (avelumab)		х	x		х	x						Required only for first 4 avelumab infusions, as needed thereafter. See Section 6.5.5.
Avelumab		x	x		x	x	x					800 mg iv Q2W until PD. For post-PD treatment, see Section 6.6.6. For post-CR treatment, see Section 4.1.1.2.
Signed Informed Consent	X											
Inclusion/Exclusion Criteria	х	x										
Demography	X											
Medical History	X											
β-HCG Pregnancy Test (if applicable)	x	x			x		Q4W		x			Serum β-HCG at Screening (can be up to 28 days prior to the first administration of study interventions); urine β-HCG thereafter for WOCBP. Results of most recent pregnancy test should be available prior to administration of study intervention.
FSH (if applicable)	X											See Section 8.2.5, Appendix 3 and Appendix 6.

		Treat	ment l	Perio	d: M3	814+	avelumab	End	of Trea	tment	(EoT)/FU	Notes
Study Period	Screening	DL	T Peri	od				EoT	Safet	ty FU	Long-term FU	
Visit	-1	1	2	3	4	5	n				Q12W	During on-treatment period, after Day 29, visits will be every 2 wks on days of avelumab
Study Day (± Visit window)	-28 to -1	1	15 (± 1)	22 (± 1)	29 (± 1)	43 (± 1)	n + 14 d (± 2)	(Within 7 days of decision to disconti nue)		≘ 90 d (± 5)	(± 7)	infusions until EoT. All participants discontinuing study interventions for any reason must undergo EoT Visit within 7 days after decision to discontinue study interventions, but (if possible) before any new antineoplastic therapy is started. The safety follow-up period will be 30 days (± 5 days) after the last dose of avelumab, see Section 4.1.1.3.

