Study Day (± Visit window)	-28 to -1	1	15 (± 1)	22 (± 1)		43 (± 1)	n + 14 d (± 2)	(Withi n 7 days of decisi on to discon tinue)	30 d (± 5)	2 90 d (± 5)	(± 7)	visits will be every 2 wks on days of avelumab infusions until EoT. All participants discontinuing study interventions for any reason must undergo EoT Visit within 7 days after decision to discontinue study interventions, but (if possible) before any new antineoplastic therapy is started. The safety follow-up period will be 30 days (± 5 days) and 90 days (± 5 days) after the last dose of avelumab, see Section 4.1.1.3
M3814		Contin	nuou	s BID	dosi	ing (7	days/wk)					See Section 6.6.5.1 for details.
Premedication (avelumab)		х	х		x	x						Required only for first 4 avelumab infusions, as needed thereafter. See Section 6.5.5.
Avelumab		х	х		X	x	x					800 mg iv Q2W until PD. For post-PD treatment, see Section 6.6.6. For post-CR treatment, see Section 4.1.1.2.
Breakfast at site		x		X								See Section 6.6.5.3 for details on breakfast composition.
Signed Informed Consent	X											
Inclusion/Exclusion Criteria	X	x										
Demography	X											
Medical History	X											
β-HCG Pregnancy Test (if applicable)	x	x			x		Q4W		X			Serum β-HCG at Screening (can be up to 28 days prior to the first administration of study interventions); urine β-HCG thereafter for WOCBP. Results of most recent pregnancy test should be available prior to administration of study intervention.

Study Period	Screening	Treatn	nent l	Perio	d: M3	3814+	avelumab	elumab End of Treatment (EoT)/FU				Notes
Study Period	Sciecining	DL1	Peri	od				EoT	Safe	ety FU	Long-term FU	
Visit	-1	1	2	3	4	5	n				Q12W	During on-treatment period, after Day 29,
Study Day (± Visit window)	-28 to -1	1	15 (± 1)				n + 14 d (± 2)	(Withi n 7 days of decisi on to discon	30 d (± 5)	全 90 d (± 5)	(± 7)	visits will be every 2 wks on days of avelumab infusions until EoT. All participants discontinuing study interventions for any reason must undergo EoT Visit within 7 days after decision to discontinue study interventions, but (if possible) before any new antineoplastic therapy is started.
								tinue)				The safety follow-up period will be 30 days (± 5 days) and 90 days (± 5 days) after the last dose of avelumab, see Section 4.1.1.3
M3814		Conti	nuou	s BID	dosi	ing (7	days/wk)					See Section 6.6.5.1 for details.
Premedication (avelumab)		x	x		x	x						Required only for first 4 avelumab infusions, as needed thereafter. See Section 6.5.5.

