4.1.1.3 Follow-Up Periods

Safety Follow-up

Part A, Part B, and Part FE

The Safety Follow-up period will be 30 days and 90 days after the last dose of avelumab for safety evaluation of the combination of study interventions.

Part B

In addition to the Safety Follow-up relating to the combination of study interventions after the last dose of avelumab, for Part B, the following RT Safety Follow-up periods are defined to assess potential toxicity of RT when administered in combination with M3814 and avelumab:

- Short-term RT Safety Follow-up: 30 days after the end of RT for evaluation of safety.
- Mid-term RT Safety Follow-up: 3 months after the end of RT to evaluate late signs of RT-induced toxicity on normal surrounding tissues.
- Long-term RT Safety Follow-up: 12 months after the end of RT, to evaluate RT-induced toxicities, by telephone call.

Long-Term Follow-up

Part A, Part B, and Part FE

Participants will be followed for survival and use of subsequent anticancer therapy until the end of the study. Participants without PD who are not receiving subsequent anticancer therapy after the End of Treatment Visit, will be followed every 8 weeks with radiographic disease evaluation for the first 6 months of the study and then every 12 weeks thereafter until PD according to Response Evaluation Criteria in Solid Tumors Version 1.1 (RECIST v 1.1), and for survival and use of subsequent anticancer therapy until the end of the study.

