- Adequate hepatic function defined by a total bilirubin level ≤ 1.5 × the upper limit of normal range (ULN), an AST level ≤ 3 × ULN, and an ALT level ≤ 3 × ULN or, for

participants with documented metastatic disease to the liver, AST and ALT levels \leq 5 × ULN. Participants with documented Gilbert disease are allowed if total bilirubin is less than 3 × ULN.

 Adequate renal function defined by an estimated creatinine clearance ≥ 30 mL/min according to the Cockcroft-Gault formula or by 24-hour urine collection for creatinine clearance or according to local institutional standard method.

Sex

- Are male or female
 - a. Male participants:

Agree to the following during the intervention period and for at least 90 days (a spermatogenesis cycle) after the last dose of study intervention:

Refrain from donating sperm

PLUS, either:

Abstain from any activity that allows for exposure to ejaculate

OR

- Use a male condom:
 - When having sexual intercourse with a woman of childbearing potential (WOCBP), who is not currently pregnant, and advise her to use a highly effective contraceptive method with a failure rate of < 1% per year, as described in Appendix 3, since a condom may break or leak.
 - When engaging in any activity that allows for exposure to ejaculate.
- b. Female participants:
- Are not pregnant or breastfeeding, and at least one of the following conditions applies:
 - Not a WOCBP, as defined in Appendix 3

OR

- If a WOCBP, use a highly effective contraceptive method (i.e., with a failure rate of < 1% per year), preferably with low user dependency, as described in Appendix 3 for the following time periods:
 - Before the first dose of the study intervention(s), if using hormonal contraception:
 - Has completed at least one 4-week cycle of an oral contraception pill and either had or has begun her menses

OR

 Has used a depot contraceptive or extended-cycle oral contraceptive for least 28 days and has a documented negative pregnancy test using a highly sensitive assay.

AND

- A barrier method, as described in Appendix 3.
- During the intervention period
- After the study intervention period (i.e., after the last dose of study intervention is administered) for at least 90 days after the last dose of study intervention and agree not to donate eggs (ova, oocytes) for reproduction during this period.

The Investigator evaluates the effectiveness of the contraceptive method in relationship to the first dose of study intervention.

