The solubility of M3814 is pH dependent; therefore, antacid drugs, H2-blocker and proton pump inhibitors (PPI) might affect absorption. PPIs should be stopped 5 days prior to the first treatment and avoided during the entire treatment period with study intervention. Antacid drugs should not be taken 1 hour before study intervention administration until 2 hours after study intervention administration. H2 blockers may be allowed but should be taken at least 2 hours after M3814 dose and stopped at least 6 hours before the next dose of M3814.

Any additional concomitant therapy that becomes necessary during the study and any change to concomitant drugs must be recorded in the corresponding section of the eCRF, noting the name, dose, duration, and indication of each drug.

If the administration of a nonpermitted concomitant drug becomes necessary during the study, e.g. because of AEs, suspension of the participant from treatment should be performed. The requirement to discontinue the participant from treatment should be discussed with the Sponsor. In case of discontinuation and where possible, the End of Treatment Visit and Safety Follow-up Visit and phone call 30 and 90 days after end of treatment should be performed as per Schedule of Activities (Table 1, Table 2, Table 3, and Table 4). Furthermore, in participants who discontinue from study intervention prior to disease progression tumor assessments should continue according to the Schedule of Activities until confirmed disease progression or start of a new anticancer treatment.

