Participants may be withdrawn from one of the study interventions, e.g. in case of intolerance or toxicity clearly attributable to a specific study intervention. Participants who are partially withdrawn from one of the study interventions and continue to achieve clinical benefit may continue with the other study interventions according to schedule until the protocol-defined criteria for discontinuation from treatment are met.

If avelumab treatment is discontinued while M3814 treatment is ongoing, M3814 treatment could be continued if the Investigator believes the participant is experiencing clinical benefit from M3814 treatment.

The Schedule of Activities specifies the data to collect at study intervention discontinuation and follow-up, and any additional evaluations that need to be completed.

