### Definition of on-treatment period

The on-treatment period is defined as the time from the first dose of study treatment through the minimum of (last date of study intervention + 30 days, start day of new anti-cancer drug therapy - 1 day, death).

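### In Parts A and FE the 30- and 90-day Safety Follow-up is counted from the last avelumab dose although M3814 may continue alone, which conflicts with other anchors in the protocol and SAP and can leave little dedicated follow-up after M3814

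*Protocol*

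**What the plan says.** Protocol 6.9.1 (under Parts A and FE) and 7.1 allow staggered stopping: "If avelumab treatment is discontinued while M3814 treatment is ongoing, M3814 treatment could be continued if the Investigator believes" the participant benefits. Section 7.1 adds that participants withdrawn from one intervention "may continue with the other study interventions according to schedule until the protocol-defined criteria for discontinuation from treatment are met". The sampling plan expects this case, since Table 5 has separate end-of-treatment rows for M3814 and for avelumab.

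The follow-up rule uses avelumab alone. Section 4.1.1.3 reads: "The Safety Follow-up period will be 30 days and 90 days after the last dose of avelumab for safety evaluation of the combination of study". The notes to Tables 1 and 4 repeat it, and say that after Day 29 "visits will be every 2 wks on days of avelumab infusions until EoT".

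Other passages use a different anchor:

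- Protocol 6.5.3, on stopping after a nonpermitted drug: a Safety Follow-up Visit and "phone call 30 and 90 days after end of treatment should be performed as per Schedule of Activities".
- Protocol 5.1, contraception for women of childbearing potential: "for at least 90 days after the last dose of study intervention and agree not to donate eggs".
- Protocol 9.4.2: TEAEs run from first dose to 30 days after the last study intervention.
- SAP 9.1, end of the on-treatment period: "minimum of (last date of study intervention + 30 days, start day of new anti-cancer drug therapy - 1 day, death".

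**The concern.** The analysis window follows the last drug taken, whereas the visit meant to cover that window follows one particular drug. If M3814 outlasts avelumab, the 30-day visit and 90-day call move towards, and then into, the M3814 treatment period. Followed as written, the plan can use up its dedicated safety follow-up before the last M3814 dose.

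The 30-day visit matters most. In Tables 1 and 4 it is the only post-treatment contact with a pregnancy test and free T4/TSH; the End of Treatment column has neither. The phrase about infusion days raises a second question: on which days is a participant seen once there are no infusions? No schedule for M3814 alone is given.

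Permanent avelumab discontinuation can follow a Grade 3 or 4 infusion reaction (Table 16), a Grade 3 or 4 hepatic or pulmonary immune-related event (Table 17), or a Grade 4 adverse drug reaction (6.9.2). Some participants on M3814 alone may therefore have had recent severe toxicity, and theirs is the visit schedule left unstated.

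**Working it through.** The plan gives no figure to reproduce. The check is date arithmetic on the stated windows, then a comparison of assessment columns.

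**Inputs.** Safety Follow-up at 30 ± 5 and 90 ± 5 days after the last avelumab dose (4.1.1.3, Tables 1 and 4). End of Treatment Visit within 7 days of the decision to discontinue (Tables 1 and 4). Long-term follow-up every 12 weeks, 84 ± 7 days (Tables 1 and 4). TEAE and on-treatment window to last study intervention + 30 days (Protocol 9.4.2, SAP 9.1).

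**Assumption.** Let L be the days M3814 continues after the last avelumab dose. The documents give no value, so a range is shown.

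**Formulas.** Nominal timing relative to the last M3814 dose is 30 − L days for the visit and 90 − L days for the call. Negative values fall on treatment.

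| L (days) | 30-day visit | 90-day call |
|---|---|---|
| 0 | 30 | 90 |
| 14 | 16 | 76 |
| 28 | 2 | 62 |
| 36 | −6 | 54 |
| 85 | −55 | 5 |
| 96 | −66 | −6 |

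Using the late edge of each window, the visit is certain to fall on M3814 treatment when L > 30 + 5 = 35 days, and both contacts do when L > 90 + 5 = 95 days. For L from 36 to 85 days, the only one of the two left after M3814 is a telephone call, 54 down to 5 days after the last dose.

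**What remains after M3814 once both contacts are used up** (columns of Tables 1 and 4):

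- End of Treatment Visit: vital signs, examination, ECOG status, AEs, hematology and chemistry, urinalysis, ECG and, where required, tumor assessment. No pregnancy test, no free T4/TSH.
- Long-term follow-up: AEs, concomitant medication, tumor assessment where required, survival. No laboratory tests, vital signs or pregnancy test.
- AE reporting to the last Long-term Follow-up Visit (8.3.1).

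If the decision to stop coincides with the last M3814 dose, the End of Treatment Visit falls by day 7. At least 30 − 7 = 23 days of the TEAE window then have no scheduled laboratory test.

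**Anchors side by side.** Section 4.1.1.3 and the table notes use the last avelumab dose; 6.5.3 uses end of treatment; 5.1, 9.4.2 and the SAP use the last study intervention. They agree only when avelumab is the last drug stopped or both stop together.

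**Part B.** M3814 is given for 2 weeks only (4.1.1.2; SAP 13), so the conflict does not arise there.

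**The case against.** A reader might infer that participants on M3814 alone have no scheduled visits and no safety follow-up afterwards. The documents do not support that.

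- Section 7.1 keeps partially withdrawn participants on schedule. The visit column is headed n + 14 days and runs until End of Treatment, which is triggered by stopping study interventions rather than avelumab. Laboratory, pregnancy and thyroid tests and examinations are listed there as intervals, so the infusion-day note can fairly be read as describing the usual case.
- Imaging runs on fixed days (56, 112, 168, then every 12 weeks).
- After M3814, the End of Treatment Visit, continuing AE reporting and follow-up to resolution of toxicity (7.1) remain. Clinically significant new laboratory abnormalities are retested weekly (8.2.5).
- TEAEs are classified by date of onset or worsening (SAP 15.1), so an event 20 days after the last M3814 dose can be picked up at a later contact.
- For short M3814-alone periods both contacts still fall after M3814: at L = 14, on days 16 and 76.
- Section 6.6.6.1 requires ongoing avelumab for treatment past initial progression, which limits the group.

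All of this stands, and it narrows the point without removing it. The schedule that 7.1 refers to is the one whose note names infusion days. Section 6.5.3 covers only the nonpermitted-drug case and itself defers to the Schedule of Activities, so it adds to the conflict. No later contact replaces the pregnancy and thyroid tests of the 30-day visit.

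**Conclusion.** The point holds for Parts A and FE. The Safety Follow-up anchor is inconsistent with the analysis windows, the contraception period and Section 6.5.3, and the visit schedule on M3814 alone has to be inferred. Dedicated follow-up after M3814 shrinks as M3814-alone treatment lengthens: the clinic visit is lost beyond 35 days, and both contacts beyond 95. Those thresholds follow from the stated windows; how many participants would reach them is unknown.

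It would also go too far to say that the affected participants are mostly those who stopped avelumab for severe toxicity. The documents give neither the number nor the type of participants concerned.

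The 3- and 4-week DLT endpoints and the food-effect comparison within its 3-week period are untouched. This should be fixed for secondary safety data and participant monitoring, but it does not threaten the primary objectives.

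**What to change.** Reconcile 4.1.1.3, the notes to Tables 1 and 4, and 6.5.3 so that in Parts A and FE the 30- and 90-day Safety Follow-up is counted from the last dose of whichever study drug stops last. This matches the TEAE window and the SAP on-treatment period, so no SAP change is needed for it. Keep the checks for avelumab immune-related events at 30 and 90 days after avelumab, within the continuing visits where M3814 goes on.

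In the same table notes, state that the n + 14 day calendar, with its interval-based tests, continues until End of Treatment while any study drug is given, and that the End of Treatment Visit follows the decision to stop the last one.

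The change concerns assessment timing only and leaves treatment rules as they are. It costs amendment wording in two sections and two tables, plus a few extra visits for participants on M3814 alone.

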4.2 Scientific Rationale for Study Design

The dose escalation design proposed for this Phase I study is deemed appropriate to define the MTD and/or RP2D of M3814 (Part A and Part B) and further investigate its safety, tolerability, PK/Pd profile, preliminary antitumor activity and the effect of high-fat meal on PK of M3814 when given in combination with avelumab in participants with metastatic or advanced solid tumors (Part A and Part FE) and with avelumab and RT in participants with selected advanced or

metastatic solid tumors (Part B). An open-label design is considered appropriate for a dose escalation study.

The decision to start Part B once the first dose level in Part A is declared safe and tolerable, along with using a 2-fold lower starting dose of M3814 compared with the starting dose level in Part A, aims to mitigate a potential increase in severity or frequency of radiation toxicity which could be related to the combination of RT with avelumab and/or M3814. This conservative approach aims to minimize risk to study participants in the initial cohort of Part B.

The starting dose in Part FE will be 100 mg BID since this dose has been assessed in 4 participants in Part A and already declared safe and tolerable. Subsequent doses will be defined based on PK and safety data generated in previous cohorts of Part A and Part FE and will be within the range of doses determined as safe in Part A. Data collected from participants in Part FE will primarily be used to investigate the FE on M3814 PK. In addition, the effects of prandial state on the safety profile of M3814 along with, tolerability, Pd profile, and preliminary antitumor activity of escalating doses of M3814 when given in combination with avelumab will also be evaluated.

Additional dosing regimens of M3814 and avelumab (Part A and Part FE) or M3814, avelumab, and RT (Part B) may be introduced by protocol amendment to be explored.

An increase in the sample size for Part A, Part B, and/or Part FE of the study to accommodate additional dose levels may be added by protocol amendment.

Future dose expansion cohorts may be included by amendment to explore efficacy in selected tumor indications in Part A and/or Part B.

Part A and Part B:

The primary endpoints of occurrence of DLTs as well as the secondary endpoint of occurrence, severity and duration of treatment-emergent adverse events (TEAEs) and treatment-related AEs according to National Cancer Institute-Common Terminology Criteria for Adverse Events (NCI-CTCAE) v 5.0 are standard objective measures of safety. A 3-week (Part A) and 4-week (Part B) period has been defined as the DLT assessment period to monitor DLT over 42 doses of M3814 and 2 administrations of avelumab for Part A and 10 administrations of M3814 and 8 fractions of RT (3 Gy each) and 3 administrations of avelumab for Part B. Secondary endpoints relating to PK, immunogenicity, and confirmed objective response as assessed by the Investigator using RECIST v1.1 criteria are also standard measurements. Duration of response, PFS and OS will also be determined as secondary endpoints and will serve to assess whether the objective response is associated with lasting clinical and survival benefit.

Part FE:

The primary endpoint is to evaluate the FE (fasted/fed state) on PK of M3814. A 3-week period has been defined as the FE Assessment Period to monitor the exposure both after single and repeated administration of M3814 over 42 doses of M3814 and 2 administrations of avelumab. Secondary endpoints relating to the effects of prandial state on the safety profile of M3814 along with immunogenicity and confirmed objective response as assessed by the Investigator using RECIST v 1.1 criteria are also standard measurements. Duration of response, PFS, and OS will

also be determined as secondary endpoints and will serve to assess whether the objective response is associated with lasting clinical and survival benefit.

Part A, Part B, and Part FE:

The exploratory pharmacodynamic assessments were selected based on the known mechanism of action and effects of M3814 and are relevant to the response, safety, or resistance to the combination. These assessments will contribute to the understanding of AEs and help in the determination of the RP2D.

Participants must have histologically or cytologically proven advanced or metastatic solid tumors (Part A and Part FE) and advanced or metastatic solid tumors eligible for fractionated RT (Part B) for which no standard therapy exists, standard therapy has failed, or the participant is intolerant to or has rejected established therapy known to provide clinical benefit for their condition. Section 5.1 and Section 5.2 provide detailed inclusion and exclusion criteria, respectively.

[figure not shown]
